1.3. Overall Risk/Benefit Assessment

This study will provide information on the safety, PK, and antiviral activity of VIR-2218, an siRNA therapeutic targeting HBV, which has the potential to functionally cure chronic HBV infection alone or in combination with other treatment modalities.

The potential benefits of VIR-2218 over the current standard of care for the treatment of chronic HBV infection are:

- A pangenotypic therapy for HBV infection that is well-tolerated and administered via SC injection for a finite duration of time
- A reduction in serum HBsAg, which may break immune tolerance against HBV and lead to a functional cure

The safety profile of VIR-2218 has not yet been established. CCI [REDACTED] CCI [REDACTED] To further mitigate risk, a “sentinel” dose design will be used in Part A as follows.

- Two subjects will be randomized 1:1 to VIR-2218 or placebo and dosed concurrently
- These subjects will be monitored for 24 hours and if the investigator has no safety concerns, the other subjects in the same cohort are dosed. The remaining 6 subjects will be randomized 5:1 to VIR-2218 or placebo.

During the conduct of the study, the Sponsor will perform ongoing safety reviews and the SRC will meet to review safety data.

In summary, there is no approved therapy that reduces serum HBsAg in a significant percentage of patients. If serum HBsAg can be effectively reduced with a pangenotypic regimen, the anticipated safety profile would offer a favorable risk-benefit determinant in patients with chronic HBV infection.

2. OBJECTIVES

2.1. Part A Objectives

The primary objective is:

- To evaluate the safety and tolerability of a single dose of VIR-2218 in healthy adult subjects

The secondary objective is:

- To characterize the PK of VIR-2218 in healthy adult subjects

2.2. Part B/C Objectives

The primary objective is:

- To evaluate the safety and tolerability of multiple doses of VIR-2218 in non-cirrhotic subjects with HBeAg-negative (Part B) and HBeAg-positive (Part C) chronic HBV infection on NUC therapy

The secondary objectives are:

- To characterize the PK of VIR-2218 in non-cirrhotic subjects with chronic HBV infection on NUC therapy
- To assess the antiviral activity of VIR-2218 in non-cirrhotic subjects with chronic HBV infection on NUC therapy

CCI

3. ENDPOINTS

3.1. Part A Endpoints

The primary endpoints are:

- Incidence of AEs
- Clinical assessments including but not limited to laboratory test results

The secondary endpoints are:

- PK parameters of VIR-2218 and possible metabolites (may include, but not limited to plasma: maximum concentration, time to reach maximum concentration, area under the concentration versus time curve [to last measurable timepoint and to infinity], percent of area extrapolated, apparent terminal elimination half-life, clearance, and volume of distribution; urine: fraction eliminated in the urine and renal clearance)

3.2. Part B/C Endpoints

The primary endpoints are:

- Incidence of AEs
- Clinical assessments including but not limited to laboratory test results

The secondary endpoints are:

- PK parameters of VIR-2218 and possible metabolites (may include, but not limited to plasma: maximum concentration, time to reach maximum concentration, area under the concentration versus time curve [to the last measurable timepoint and to infinity], apparent terminal elimination half-life, clearance, and volume of distribution)
- Maximum reduction of serum HBsAg from Day 1 until Week 16
- Number of subjects with serum HBsAg loss at any timepoint
- Number of subjects with sustained serum HBsAg loss for ≥ 6 months
- Number of subjects with anti-HBs seroconversion at any timepoint
- For HBeAg-positive subjects (Part C only): number of subjects with HBeAg loss and/or anti-HBe seroconversion at any timepoint

CCI

4. STUDY DESIGN

4.1. Treatment Plan and Regimen

[figure not shown]
This is a randomized, double-blind, placebo-controlled study of VIR-2218 administered subcutaneously to healthy adult subjects and non-cirrhotic adult subjects with chronic HBV infection who are on NUC therapy. The study is designed to evaluate the safety, tolerability, PK, and antiviral activity of VIR-2218. Part A is planned to be conducted at 1 clinical investigative site; Parts B and C are planned to be conducted at multiple clinical investigative sites in the Asia-Pacific region. The study designs for Part A SAD and Part B/C MAD are presented in Figure 1 and Figure 2, respectively, and the cohort dosing schedule is provided in Appendix 6.

Figure 1. SAD Study Design for Part A

^a Subject discharge will occur after all assessments are completed on Day 2

Figure 2. MAD Study Design for Part B/C

^a Additional HBsAg monitoring is required for subjects with HBsAg levels with a > 10% decrease from the Day 1 predose level at the Week 16 visit. Visits will occur every 4 weeks starting at Week 20 up to Week 48 or until the HBsAg level returns to $\geq 90\%$ of the Day 1 predose level. Additional HBsAg monitoring may be discontinued at the Sponsor's discretion based on emerging data.

4.1.1. Part A Single Ascending Dose Phase in Healthy Adult Subjects

Healthy adult subjects will be enrolled in 1 of 4 planned ascending dose cohorts. At the start of each cohort, 2 sentinel subjects will be randomized 1:1 to VIR-2218 or placebo. These subjects will be dosed concurrently and monitored for 24 hours; if the investigator has no safety concerns, the remainder of the subjects in the same cohort will be dosed. Vital signs, symptom-directed physical examination(s), and AEs will be reviewed by the investigator prior to dosing any additional subjects. The remaining subjects will be randomized 5:1 to receive a single dose of VIR-2218 or placebo.

Subject screening will occur no more than 4 weeks prior to the Day 1 visit. Eligible subjects will be confined to the clinical investigative site on Day -1 to determine continued eligibility and for predose assessments. Subjects in each cohort will be randomized to receive VIR-2218 or placebo within 48 hours prior to study drug administration. Subjects will receive a single dose of study drug on Day 1 (VIR-2218 or placebo). Subjects will be discharged from the clinical investigative site after all assessments are completed on Day 2.

Subjects will return to the clinical investigative site on an outpatient basis for safety, tolerability, and PK monitoring at specified timepoints through the last Post-dose Follow-up Visit (Week 12).

Based on review of the accumulated, available data in Part A, the SRC may recommend dosing of 2 optional cohorts. In addition to the optional cohorts, up to 8 “floater” subjects for Part A may be added to any cohort, as determined and approved by the SRC (see Section 4.5.2 and Appendix 6 for further information).

Fasting is not required for any study procedure/assessment.

4.1.2. Part B/C Multiple Ascending Dose Phase in Non-Cirrhotic Adult Subjects with Chronic HBV Infection on Nucleoside/Nucleotide Therapy

Non-cirrhotic adult subjects with chronic HBV infection on NUC therapy for ≥ 6 months will be enrolled in the Part B/C cohorts. Part B will enroll HBeAg-negative subjects. Part C will enroll HBeAg-positive subjects. Eligible subjects should have HBV DNA < 90 IU/mL. Each cohort in Part B/C will be composed of 4 subjects randomized 3:1 to VIR-2218 or placebo, respectively. There are 3 planned and 2 optional cohorts in Part B. There are 1 planned and 2 optional cohorts in Part C.

Subjects enrolled in Part B/C of the study will remain outpatient. Subject screening will occur no more than 4 weeks prior to the Day 1 visit. Eligible subjects will undergo further assessments on Day 1 to qualify for study drug administration on Day 1. To exclude the presence of cirrhosis, screening will include a mandatory noninvasive assessment of liver fibrosis such as a FibroScan evaluation, unless the subject has results from a FibroScan evaluation performed within 6 months prior to screening or a liver biopsy performed within 1 year prior to screening that confirms the absence of Metavir F3 fibrosis or F4 cirrhosis.

Subjects in each cohort will be randomized 3:1 to receive VIR-2218 or placebo within 48 hours prior to study drug administration on Day 1. Subjects will return to the clinical investigative site at Week 4 to receive a second dose of the same study drug administered on Day 1. The decision to administer a second dose will be made based on Week 3 laboratory values in accordance with dose suspension/stopping criteria in Section 4.6.

CCI

Subjects will return to the clinical investigative site on an outpatient basis for safety, tolerability, PK, and antiviral activity monitoring at specified timepoints through the last Post-dose Follow-up Visit (Week 16). Additional HBsAg monitoring is required for subjects with HBsAg levels with a $> 10\%$ decrease from the Day 1 predose level at the Week 16 visit. Visits will occur

every 4 weeks starting at Week 20 up to Week 48 or until the HBsAg level returns to $\geq 90\%$ of the Day 1 predose level. Additional HBsAg monitoring may be discontinued at the Sponsor's discretion based on emerging data.

Based on review of the accumulated, available data in Parts A, B, and C, the SRC may recommend dosing of optional cohorts following the same stratification. In addition to the optional cohorts, a combined total of up to 16 "floater" subjects for Part B/C may be added to any cohort, as determined and approved by the SRC (see Section 4.5.5 and Appendix 6 for further information).

Fasting is not required for any study procedure/assessment. The assessments performed at each visit are described in Appendix 3 .

4.2. Discontinuations

Subjects who discontinue prematurely will be followed for safety, and under certain circumstances, subjects who discontinue study drug (as described in Section 4.3) may be replaced. If a subject discontinues from the study post-dose but before completion of the Week 12 visit for Part A or the Week 16 visit for Part B/C, an Early Termination (ET) visit should be performed.

4.3. Replacement of Subjects

Replacement subjects may be enrolled to ensure that the minimum data requirements for SRC dose escalation decisions and study progression are met, as described in Section 4.5. Subjects who do not receive the full planned dose, do not receive a second dose (for Part B/C), discontinue due to an AE that does not meet study progression/escalation and dose suspension/stopping rules (Section 4.6), or who withdraw from the study, may be replaced with confirmation by the SRC. Subjects who are discontinued from treatment for reasons other than experiencing an AE may be replaced following discussion between the Sponsor and investigator.

The replacement subject will be assigned a unique study identification number and will receive the same study drug assignment and dose level as the subject who is being replaced and in the same blinded fashion.

4.4. Safety Review Committee

A SRC will perform ongoing reviews of safety, tolerability, and available study data collected throughout the study with the primary purpose of protecting the safety of subjects participating in this clinical study. The SRC will be governed by an SRC Charter that will be finalized prior to screening the first subject.

The SRC will undertake safety data review prior to initiation of dosing a new cohort in Parts A, B, and C of the study in accordance with the SRC Charter. In addition, ad hoc SRC meetings may take place as needed, eg, for a significant safety event such as a subject or cohort stopping criterion being reached (Section 4.6).

Decisions to suspend dosing or discontinue individual subjects from study drug will be made according to predetermined stopping rules (Section 4.6). Additionally, the SRC may recommend discontinuation of the study to the Sponsor. The SRC membership composition is described in detail in the SRC Charter.

4.5. Study Drug Dosing, Study Progression, and Dose Escalation

Progression rules are based on the absence of prespecified safety signals. Standard toxicity grading according to the current Common Terminology Criteria for Adverse Events (CTCAE) Version 5 will be used to grade AEs. The decision to enroll an optional cohort or expand an existing cohort will be made by the SRC based on available safety, tolerability, and antiviral activity data, if further data are considered necessary to better understand dose response and/or safety and tolerability.

Subjects will receive VIR-2218 or placebo via SC injection according to the schedules provided in Appendix 2 and Appendix 3 for Cohort A and Cohort B/C, respectively.

4.5.1. Part A Study Drug Dosing, Study Progression, and Dose Escalation in Planned Cohorts

The starting dose for the first cohort in Part A is 50 mg, as described in Section 1.2.4. The SRC will review available laboratory and clinical safety data, including Week 4 data from the last available subject enrolled in the cohort to proceed to the next planned cohort in Part A. There are 4 planned cohorts in Part A: 50 mg, 100 mg, 200 mg, and 400 mg (Table 4).

4.5.2. Part A Optional Cohorts and Floater Subjects

Based on SRC review of accumulated safety and tolerability data, 2 optional cohorts may be enrolled and dosed according to the same eligibility criteria and corresponding randomization scheme to better define safety and tolerability. The maximum optional dose in Part A will not exceed the defined maximum administered single dose of 900 mg (see Appendix 6 for additional information).

In addition to the optional cohorts, up to 8 “floater” subjects in total for Part A may be added to expand any of 6 possible cohorts (planned or optional), as determined and approved by the SRC. Each expansion must include a minimum of 4 “floater” subjects, randomized 3:1 to VIR-2218 or placebo, furthermore only half of the total “floater” subjects (4 subjects in Part A) may enroll in the highest optional dose cohort.

4.5.3. Part B Study Drug Dosing, Study Progression, and Dose Escalation in Planned Cohorts

Overview: There are 3 planned cohorts in Part B: 50 mg, 100 mg, and 200 mg. Part B is limited to subjects with chronic HBV infection who are HBeAg-negative. Each cohort will receive a dose on Day 1, and a second dose at Week 4, such that the cumulative dose received for the planned cohorts in Part B will be 100 mg, 200 mg, and 400 mg (Table 4).

Initiation of Part B: 2 dose levels in Part A (1a: 50 mg and 2a: 100 mg) must be completed and cumulative safety data, inclusive of the clinical and laboratory data from Week 4 from the last subject dosed in Cohort 2a (100 mg), must be reviewed by the SRC to begin dosing Part B (1b: 50 mg).

Escalation within Part B: Escalation to a higher dose-level cohort will only occur after the SRC has reviewed clinical and laboratory data including data from the Week 6 visit of the last available subject in the ongoing cohort, and the subject has completed their Week 8 visit. The SRC may review cumulative data from subjects in Parts A, B, and C at the time of meeting. The SRC will ensure that no subject in a cohort from Part B will receive a particular dose level prior to review of Week 4 data from subjects in Part A who have received at least the same cumulative dose level.

CCI

4.5.4. Part C Study Drug Dosing, Study Progression, and Dose Escalation in Planned Cohorts

Overview: There is 1 planned cohort in Part C: 200 mg (Cohort 3c). Escalations to higher dose levels may only occur in the optional cohorts (Section 4.5.5). Part C is limited to subjects with chronic HBV infection who are HBeAg-positive. This cohort will receive a dose on Day 1, and a second dose at Week 4, such that the cumulative dose received will be 400 mg (Table 4).

Initiation of Part C: The planned Cohort 3c will initiate at the same time as Cohort 3b (200 mg, given as 2 doses, 4 weeks apart), after the SRC has reviewed clinical and laboratory data including from the Week 6 visit of the last available subject in Cohort 2b. Initiation of Cohort 3c will not occur until the last available subject in Cohort 2b has completed their Week 8 visit.

4.5.5. Part B/C Optional Cohorts and Floater Subjects

Based on SRC review of accumulated safety and tolerability data, up to 2 optional dose-level cohorts may be enrolled and dosed in each study part according to the randomization scheme to better define dose response and/or safety and tolerability. Enrollment of the Part B/C optional cohorts will be according to the same Part B/C eligibility criteria as the planned cohorts.

The optional cohorts may be dosed at lower, intermediate, and/or higher dose levels than the dose levels explored in the planned Part B or C cohorts. The maximum cumulative dose level in any cohort in Part B or C will not exceed the highest single dose found to be well tolerated in Part A. For example, if a single dose of 900 mg in Part A is determined by the SRC to have an acceptable safety profile, dose levels of 450 mg (cumulative dose of 900 mg) or lower dose levels can be explored in Part B/C. The maximum administered cumulative dose in any cohort will not exceed 900 mg (Table 4).

Dose escalation in the optional Part B/C cohorts will occur according to the same criteria as dose escalation within Part B (Section 4.5.3.)

In addition to the optional cohorts, up to 16 “floater” subjects in total for Part B/C may be added to expand any Part B or C cohort (planned or optional), as determined and approved by the SRC. This “floater” pool is shared between Part B/C and the allocation of floater subjects does not need to be distributed evenly across parts. Subjects will be added in increments of 4 and randomized 3:1 to VIR-2218 or placebo, furthermore only half of the total “floater” subjects (8 total subjects in Part B/C) may enroll in the highest optional dose cohort.

4.6. Stopping Rules

The following stopping rules are based on potential safety signals. Standard toxicity grading according to the CTCAE Version 5.0 will be used to grade AEs. When a cohort is stopped, no further study drug will be administered at the dose level and further dose escalation/progression will be suspended. An ad hoc SRC meeting will be held, and only following SRC approval, may dosing be resumed at the same or a higher dose level; if required, additional approval from the concerned regulatory authority and the independent ethics committee (IEC)/institutional review board (IRB), in accordance with applicable requirements, will be obtained. De-escalation to a lower dose will be allowed at Sponsor discretion.

4.6.1. Cohort Stopping Rules

If any of the criteria described below are met, cohort dosing will be suspended or stopped:

- Part A only: If a sentinel subject experiences a VIR-2218-related Grade 3 or higher AE
- If 1 or more subjects experience a Grade 3 VIR-2218-related rash
- If 2 or more subjects experience the same VIR-2218-related Grade 3 or higher AE
- If 1 or more subjects experience a VIR-2218-related serious adverse event (SAE)
- If 1 or more subjects experiences a Grade 4 AE of rash, regardless of assessed causality

4.6.2. Individual Subject Stopping Rules in Part B/C

Individual subjects in Part B/C who have received 1 dose of study drug will not receive a second dose if any the following criteria are met:

- Serum ALT > 10 × ULN
- Serum ALT > 5 × ULN, with no change (< 50% of baseline) in HBsAg
- Serum ALT or AST > 3 × ULN with a concomitant total bilirubin > 2 × ULN
- Any clinical manifestations of hepatic decompensation

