7.2.7. Clinical Laboratory Assessments

Clinical laboratory tests that will be performed in this study are presented in Table 6. In the event of an unexplained clinically relevant abnormal laboratory test occurring after study drug administration, the test should be repeated and followed up at the discretion of the investigator until it has returned to the normal range or stabilized, and/or a diagnosis is made to adequately explain the abnormality.

Table 6. Clinical Laboratory Tests

Hematology	
• Complete blood count with differential	
Chemistry	
• Albumin	• Creatinine clearance
• Blood urea nitrogen (BUN)	• Gamma glutamyl transferase (GGT)
• Calcium	• Glucose
• Carbon dioxide/bicarbonate	• Lactate dehydrogenase (LDH)
• Chloride	• Potassium
• Creatine kinase ^a	• Sodium
• Creatinine	• Uric acid
Liver Function Tests	
• Alkaline phosphatase (ALP)	• AST
• ALT	• Bilirubin (total and direct)
Coagulation Parameters	
• International normalized ratio (INR) time	• Prothrombin
Urinalysis	
• Bilirubin	• Proteins
• Glucose	• Red blood cells (RBCs)
• Ketones	• Screen for drugs of abuse
• Leukocytes	• Specific gravity
• Microscopy (if clinically indicated)	• Urobilinogen
• Nitrite	• Visual inspection for appearance and color
• pH	
Pregnancy Testing	
• Beta-human chorionic gonadotropin (WOCBP only)	• Urine pregnancy test
Serology	
• Hepatitis B, C, and Delta	• Human immunodeficiency virus I and II

^a Only required if ALT and/or AST is elevated 2 × higher than predose Day 1 baseline value

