Alcohol intake assessment ^g		X		X	X	X	X	X	X	X	X	X	X	X	X	X
Body weight	X															
Height and BMI	X															
Vital signs ^h	X	X	X	X	X	X	X	X	X	X	X	X	X			
Safety ECG ⁱ	X	X	X				X									
Pregnancy test ^j	X	X					X				X	X	X			
FibroScan ^k	X															
Screening viral serology ^l	X															
Laboratory assessments ^m	X	X	X	X	X	X	X	X	X	X	X	X	X	X ⁿ	X ⁿ	X ⁿ
Urinalysis ^m	X	X														

Part B/C																
Study Stage	Screening	Dosing Period						Post-dose Follow-up Period ^b						Extended Follow-up Period ^c		
Study Visit Week				W1	W2	W3	W4 ^a	W5	W6	W7	W8	W12	W16	W20	W24	
Study Visit Day ± Visit Window	D -28 to -1	D1 ^a	D2	D8 ±2	D15 ±2	D22 ±2	D29 ^a ±2	D36 ±2	D43 ±2	D50 ±2	D57 ±2	D85 ±7	D113 ±7/ET	D141 ±7	D169 ±7	Q28D ±7
Urine for drugs of abuse ^o	X															
Randomization		X														
Study drug administration ^p		X					X									
Blood samples for PK analysis ^q		X	X	X			X ^r	X								
Blood sample for HBsAg	X	X	X	X	X	X	X	X	X	X	X	X	X	X	X	X
Blood sample for anti-HBs	X										X		X		X	X ^s
Blood sample for HBeAg qualitative	X															
Blood sample for HBeAg quantitative for Part C only ^t		X					X				X	X	X		X	X ^s
Blood sample for anti-HBe for Part C only	X										X		X		X	X ^s
Blood sample for HBV DNA quantitation ^u	X	X					X				X	X	X	X	X	X ^s
CCI																

Part B/C																
Study Stage	Screening	Dosing Period						Post-dose Follow-up Period ^b						Extended Follow-up Period ^c		
Study Visit Week				W1	W2	W3	W4 ^a	W5	W6	W7	W8	W12	W16	W20	W24	
Study Visit Day ± Visit Window	D -28 to -1	D1 ^a	D2	D8 ±2	D15 ±2	D22 ±2	D29 ^a ±2	D36 ±2	D43 ±2	D50 ±2	D57 ±2	D85 ±7	D113 ±7/ET	D141 ±7	D169 ±7	Q28D ±7
CCI																
Review/Record AEs ^x	X															
Concomitant Medications	X															
NUC medication adherence	X															

AE = adverse event; ECG = electrocardiogram; ET=end of treatment; **CCI** HBeAg = hepatitis e-antigen; HBsAg = hepatitis B surface antigen; HBV = Hepatitis B Virus; NUC = nucleoside/nucleotide; PK = pharmacokinetics; MAD = multiple ascending dose

Note: When scheduled at the same timepoints, the assessments of vital signs and 12-lead ECGs must be performed first, before the physical examinations, blood sample collections, and urine collections.

^a Assessments performed predose unless otherwise specified.

^b If a subject withdraws prematurely from the study prior to their Week 16 visit, ET assessments should be performed.

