^c Additional HBsAg monitoring is required for subjects with HBsAg levels with a > 10% decrease from the Day 1 predose level at the Week 16 visit. Visits will occur every 4 weeks starting at Week 20 up to Week 48 or until the HBsAg level returns to ≥ 90% of the Day 1 predose level. For example, if Day 1 predose HBsAg is 560 IU/mL and Week 16 HBsAg is 490 IU/mL, the subject will be followed until HBsAg levels returns to ≥ 504 IU/mL. Additional HBsAg monitoring may be discontinued at the Sponsor’s discretion based on emerging data.

^d A complete medical history will be taken at screening including HBV genotype if available. Any changes should be updated prior to dosing.

^e Evaluation of inclusion criteria related to urine pregnancy testing and urine drug screen.

^f See Section 7.2.1 for assessments to be performed during a full physical examination.

^g Subjects’ alcohol intake will be recorded while on study.

^h Vital signs (blood pressure, pulse rate, respiratory rate, and temperature) should be measured in the supine position after the subject has rested comfortably for approximately 10 minutes. On Day 1, vital signs should be measured within 2 hours predose and 4 hours post-dose. On all other visit days, vital signs are only required to be recorded once during the visit.

ⁱ 12-lead safety ECGs will be recorded on the timepoints listed in Appendix 5 and should be measured in the supine position after the subject has rested comfortably for 10 minutes.

^j WOCBP are required to have pregnancy tests. A serum pregnancy test will be performed at screening and urine pregnancy tests will be performed thereafter. Negative pregnancy test must be confirmed prior to study drug administration.

^k Does not need to be performed if the subject has had a FibroScan in the 6 months prior to screening or liver biopsy in the year prior to screening that confirmed the absence of Metavir F3 fibrosis or F4 cirrhosis.

^l See Section 7.1.3 for viral serology parameters.

^m Clinical laboratory and urinalysis parameters are described in Section 7.2.8.

ⁿ Liver function tests only.

^o Drugs of abuse included in the screen are described in the inclusion/exclusion criteria. Screening results for drugs of abuse must be reviewed prior to dosing.

^p Study drug will be administered via SC injection as described in Section 6.2.4.

^q Blood samples for PK analysis will be collected at the timepoints listed in Appendix 5.

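### The ALT > 5 × ULN rule for withholding dose 2 gives no direction for the HBsAg change, so on one natural reading a large HBsAg rise escapes the stop

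*Protocol*

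**What the plan says.** Protocol 4.6.2 lists four criteria, any one of which means that a Part B/C subject does not get the second dose. Three do not depend on HBsAg: ALT above 10 × ULN; ALT or AST above 3 × ULN with total bilirubin above 2 × ULN; and clinical hepatic decompensation. The fourth is ALT above 5 × ULN "with no change (< 50% of baseline) in HBsAg". No direction is attached to the change.

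The line governs dosing. Protocol 4.1.2 states: "The decision to administer a second dose will be made based on Week 3 laboratory values", and ties that decision to Section 4.6. Protocol 4.4 likewise has individual discontinuations follow the predetermined stopping rules.

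Elsewhere the protocol does give HBsAg a direction. Appendix 3, footnote c, starts extended follow-up for "HBsAg levels with a > 10% decrease from the Day 1 predose level", and a secondary endpoint in 3.2 is "Maximum reduction of serum HBsAg from Day 1 until Week 16". The SAP does not restate the stopping rule; it refers back to the protocol.

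**The concern.** A hepatic stopping rule should give one answer for one set of laboratory values, and it should not become more permissive as the HBsAg result moves further the wrong way. As worded, the line secures neither. Parts B and C run at multiple sites, so two sites could handle identical Week 3 results differently.

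On the absolute-change reading, a rise of 50% or more counts as a change, so the criterion is not met. A subject with raised ALT whose HBsAg has climbed steeply would then face no mandatory stop, while one with a smaller rise would. That is hard to square with a drug whose expected effect is to lower HBsAg. At stake is whether such a subject is given a second dose.

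**Working it through.** There is no sample size, power or error-rate figure behind this line, so there is nothing of that kind to reproduce. The check is to enumerate what the rule does under each reading.

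**Inputs**
- Day 1 HBsAg of 560 IU/mL: the worked example in Appendix 3, footnote c ("if Day 1 predose HBsAg is 560 IU/mL").
- ALT of 7 × ULN at Week 3: an illustrative value in the band above 5 and up to 10 × ULN, where only the HBsAg-dependent criterion decides.
- Assumed: AST and bilirubin do not meet the combined criterion, and there is no decompensation.

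**Readings**, with r = Week 3 HBsAg ÷ Day 1 HBsAg:
- A, absolute change below 50%: stop if |r − 1| < 0.5, that is 280 < HBsAg < 840.
- B, fall below 50%: stop if 1 − r < 0.5, that is HBsAg > 280.
- C, signed change below 50% (result minus baseline, as SAP 3.2 defines change): stop if r − 1 < 0.5, that is HBsAg < 840.
- D, level below 50% of baseline: stop if r < 0.5, that is HBsAg < 280.

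Cut-offs: 0.5 × 560 = 280 and 1.5 × 560 = 840.

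| Week 3 HBsAg (IU/mL) | Change | A | B | C | D |
|---|---|---|---|---|---|
| 112 | −80% | no stop | no stop | stop | stop |
| 280 | −50% | no stop | no stop | stop | no stop |
| 336 | −40% | stop | stop | stop | no stop |
| 560 | 0% | stop | stop | stop | no stop |
| 784 | +40% | stop | stop | stop | no stop |
| 840 | +50% | no stop | stop | no stop | no stop |
| 896 | +60% | no stop | stop | no stop | no stop |
| 1120 | +100% | no stop | stop | no stop | no stop |

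A rise of 50% or more meets the stop only under B, which needs a word that the text lacks. A and B, the two most natural readings, differ only at 840 IU/mL and above. C and D also differ from them for large falls. D fits poorly, because the bracket is there to explain an absence of change. For a subject at the entry limit of 150 IU/mL, the cut-offs are 0.5 × 150 = 75 and 1.5 × 150 = 225.

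Outside this ALT band the ambiguity has no effect. At 4 × ULN neither ALT-only nor ALT-with-HBsAg criterion is met under any reading; at 11 × ULN every reading stops.

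**Do the cohort rules catch this subject?** Taking one non-serious, non-rash event in Part B/C through Protocol 4.6.1:
- The sentinel rule is for Part A only.
- Two rules concern rash.
- One needs a drug-related serious event.
- The general rule reads: "If 2 or more subjects experience the same VIR-2218-related Grade 3 or higher AE". One subject does not meet it.

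Protocol 8.1.1 also keeps laboratory abnormalities without signs or symptoms from being recorded as adverse events, so an asymptomatic ALT rise may not count toward any of these rules. The HBsAg-dependent line in 4.6.2 is then the only mandatory rule in play.

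**The case against.** The strongest reply is that context supplies the direction. The protocol presents HBsAg reduction as what sets the drug apart, as the hoped-for benefit and as an endpoint, so a trained investigator would probably take the phrase to mean no HBsAg response. Nothing in the documents shows a site reading it otherwise. This has force, and it is why fall-only is the likely intent. It remains an inference, and a dosing rule should not rest on one.

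A reader might go further and call the rule wrong as written. The documents do not support that. They give no rationale for the HBsAg condition. An either-direction reading is also coherent: a large movement either way might be taken to suggest a virus-related flare, and a flat HBsAg some other cause. That too is inference, but it means the line is unclear and not shown to be an error.

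A reader might also infer that a subject in the gap must be dosed. Section 4.6.2 says when dose 2 is withheld; it does not oblige dosing otherwise. The sponsor performs ongoing safety reviews (1.3), clinically relevant abnormal results are repeated and followed (7.2.7), an ALT above 2 × ULN may prompt extra HBV DNA sampling (Appendix 3), and the SRC may meet ad hoc (4.4). These safeguards stand, though they are discretionary or do not themselves mandate a stop.

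Finally, one might object that baseline is undefined in 4.6.2. That is a weak point. Table 6 uses "predose Day 1 baseline value" and SAP 3.2 defines baseline as the last valid predose observation. The SAP definition governs analysis and not dosing, but there is little doubt about what is meant.

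**Conclusion.** The ambiguity is real. Neither document gives a direction, and the line feeds the Week 3 dosing decision. On the absolute-change reading the stop applies at a 40% HBsAg rise and lapses at a 60% rise, with no other mandatory rule covering that subject.

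Its reach is small. It needs isolated ALT above 5 and up to 10 × ULN together with an HBsAg rise of at least 50% at Week 3, in at most 48 Part B/C subjects who enter on NUC therapy with HBV DNA below 90 IU/mL and ALT and AST no higher than 2 × ULN. The documents give no frequency; I expect the case to be rare. Endpoints, analyses and sample size are unaffected.

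This is worth clarifying at low priority. It rests on two assumptions: that large falls alone were meant to be exempt, and that the protocol supplied is the version in force. The second is open. SAP 2.1 cites the stopping rules as protocol Section 4.8 and mentions Parts D to F, which this protocol does not contain.

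**What to change.** First check whether another protocol version already words the line with a direction, and have the sponsor confirm that only falls were meant to be exempt. If so, replace the second criterion in 4.6.2 with:

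*Serum ALT > 5 × ULN without a ≥ 50% decrease in HBsAg from baseline (Day 1 predose, or the last available predose value if missing); any increase counts as no decrease.*

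This keeps the 50% threshold and the Week 3 decision point, and settles all four readings. In the 560 IU/mL example it stops dosing at any Week 3 value above 280 IU/mL. The fallback for a missing Day 1 sample is workable because HBsAg is also drawn at screening.

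The cost is one line in a clarification letter or the next amendment. No visit, sample or analysis changes: the Appendix 3 row "Blood sample for HBsAg" already includes Week 3. The only downside is that a rare subject with a large HBsAg rise would have dose 2 withheld, and Protocol 4.3 already allows a subject who misses the second dose to be replaced with SRC confirmation.
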